1. LIST OF ABBREVIATIONS

Abbreviation	Definition
ADR	Adverse Drug Reaction
AE	Adverse Event
CGI-I	Clinical Global Impression-Improvement
CRF	Case Report Form
IEC	Independent Ethics Committee
IRB	Institutional Review Board
LSLV	Last Subject Last Visit
MDD	Major Depressive Disorder
MFDS	Ministry of Food and Drug Safety
PCD	Primary Outcome Completion Date
PMS	Post Marketing Surveillance
SAE	Serious Adverse Event
SRSD	Single Reference Safety Document

3. AMENDMENTS AND UPDATES

Amendment number	Date	Substantial or administrative amendment	Protocol section(s) changed	Summary of amendment(s)	Reason
Amendment 1	5Mar2015	Substantial	7.1. 7.3.3.1. 7.7.	Convert study design prospectively. Add long-term use study. Add separate analysis in special subject group.	following the guideline of post-marketing surveillance
Amendment 2	11Nov2015	Substantial	1. 4. 6. 7. 8. 9. Entire document	Add abbreviations. Add milestones and modify planned dates. Change MFDS Notification No. Clarify descriptions for research methods, subject exclusion criteria, subject observation period, effectiveness and safety assessment and modify/add minor wording. Modify minor wording. Modify/add/delete some phrases following the Pfizer template and modify minor wording. Change MFDS Notification No. Modify terminology following the revised MFDS Notification.	Modifying contents requiring clear description among the protocol contents
Amendment 3	14Jan2016	Substantial	7.4.9.1. Entire document	Modify the period within which CGI-I evaluation is allowed in case of withdrawal from 'within 6 weeks of the last administration' to 'within 2 weeks of the last administration'. Modify '28 calendar days' to '28 days'.	Reflecting MFDS recommendations
Amendment 4	29Mar2016	Administrative	7.4.10.2 9.1 9.4.3	Clarify the Korean translation of some phrases following the Pfizer template (English) regarding the safety reporting requirement (Korean version only). Clarify the Korean translation of some phrases following the Pfizer template (English) regarding the safety reporting requirement (Korean version only). Modify or add some phrases following the Pfizer template (English) regarding the safety reporting requirement. Modify the Korean translation of some phrases following the Pfizer template (English) regarding the safety reporting requirement (Korean version only). Add the definition of 'lack of efficacy'.	Keeping consistency with the Pfizer template (English) regarding the safety reporting requirement and clarifying the definition of 'lack of efficacy'

4. MILESTONES

Milestone	Planned date
Data collection start date	01 Dec 2015
Data collection end date	01 Dec 2018
MFDS interim report 1-1	05 Oct 2014
MFDS interim report 1-2	05 Apr 2015
MFDS interim report 2-1	05 Oct 2015
MFDS interim report 2-2	05 Apr 2016
MFDS interim report 3	05 Apr 2017
MFDS interim report 4	05 Apr 2018
MFDS interim report 5	05 Apr 2019
MFDS re-examination report	05 May 2020

5. RATIONALE AND BACKGROUND

The objective of the Re-examination system in Korea is to re-confirm the clinical usefulness of the product through collecting, reviewing, identifying and verifying the safety and effectiveness information about the product in general practice (usually for a period of 6 years after the product is registered).

PRISTIQ® (desvenlafaxine) is classified as a dual acting Serotonin and Norepinephrine Reuptake Inhibitor (SNRI). Desvenlafaxine extended-release tablets are indicated for the treatment of major depressive disorder (MDD) in adults and for the treatment of moderate to severe vasomotor symptoms (VMS) associated with menopause.

PRISTIQ® was approved by Ministry of Food and Drug Safety (MFDS) in Korea on 06 Feb 2014 for the treatment of Major Depressive Disorder (MDD). This surveillance is conducted for preparing application material for re-examination under the Pharmaceutical Affairs Laws and its Enforcement Regulation, and observation of safety and effectiveness of PRISTIQ® in usual practice according to the Re-examination Guideline of New Drugs, Etc.

The re-exam period for PRISTIQ® is from 06 February 2014 to 05 February 2020, and the final study report should be submitted by 05 May 2020. The analyzed study report based on collected data of 6 years must be submitted to MFDS within 3 months after the end of specified re-examination period (from the product approval date to 6 years afterwards).

6. RESEARCH QUESTION AND OBJECTIVES

The objectives of this study are to determine any problems or questions associated with PRISTIQ® after marketing, with regard to the following clauses under conditions of general clinical practice, in compliance with the regulation “Re-examination Guideline of New Drugs, Etc” (Ministry of Food and Drug Safety Notification 2015-79, 2015.10.30, amended).

- (1) Serious adverse event/adverse drug reaction
- (2) Unexpected adverse event/adverse drug reaction that has not been reflected in the approved drug label.
- (3) Known adverse drug reaction
- (4) Non-serious adverse drug reaction
- (5) Other safety and effectiveness information

7. RESEARCH METHODS

7.1. Study Design

This study is open-label, non-comparative, observational, non-interventional, prospective and multi-center study in which subjects are administered PRISTIQ® as part of routine practice at Korean health care centers by accredited psychiatrists. The observation period for each subject is from initiating administration of PRISTIQ® until week 8. If administration is discontinued before week 8, observation should be done for at least 28 days from the last administration day. There will be no visit or activity mandated by this study and routine observation will be done during the above-mentioned period.

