7.3.3. Duration of the study

According to MFDS re-examination regulation, the re-examination report based on collected data of 6 years must be submitted to MFDS within 3 months after the end of specified re-examination period (from the product approval date to 6 years afterwards). The re-exam period is from 06 February 2014 to 05 February 2020, and the final study report should be submitted by 05 May 2020.

The data collection period of this study is until the required subject number (600 patients) is collected. The observation period for each subject is from initiating administration of PRISTIQ® until week 8. If administration is discontinued before week 8, observation should be done for at least 28 days from the last administration day. All the data collected during the observation period should be recorded in the case report form (CRF). In case of an adverse event/safety event recognized after the observation period ends, it should be recorded in the CRF as specified in Section 9.

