7.3.3.1. Long-term use study

As PRISTIQ® could be used in a long time considering its indication, data from the patients administered in a long time out of enrolled patients will be collected and analyzed separately. Safety and effectiveness data of at least 60 subjects who have been administered PRISTIQ® over 6 months out of enrolled subjects will be collected.

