7.4.10.3. Adverse events data collection

The investigator collects data on safety events as specified in Section 9 including all adverse events that occur during the observation period regardless of causal relationship to PRISTIQ®. The information on adverse events should include the specific conditions or events, duration of the events (start date and stop date), seriousness (serious or non-serious), severity, causal relationship to PRISTIQ®, actions taken, and outcome.

Check either 'yes' or 'no' in adverse event occurrence section. If 'yes', record in detail.

- Adverse event: Record the term of adverse event. If possible, specify diagnosis, not individual symptoms.
- Date of onset: Record the date of onset.
- Severity: Severity evaluation of adverse events must be done according to the following category.

1. Mild- Not causing any significant problem to the subject; Continuous medication of study drug is possible without dose adjustment.
2. Moderate- Cause a problem that does not interfere significantly with usual activities or the clinical status; Dose adjustment of study drug or other therapy is needed due to adverse event.
3. Severe- Cause a problem that interferes significantly with usual activities or the clinical status; Study drug should be stopped due to adverse event.

If the severity of an adverse event changed, the adverse event must be entered separately. Record stop date of previous severity and onset date of new severity – along with completion of all other items.

- Action: Check all relevant actions.

1) PRISTIQ®: Check the appropriate number for the adjustment of PRISTIQ® resulted from the adverse event.

1. Withdrawn (temporarily or permanently, or delayed)
2. Dose reduced
3. Dose increased
4. Dose not changed
5. Unknown
6. Not applicable

2) Others: After the onset of adverse event, the investigator should indicate other actions taken and record in detail.

1. Treatment given (please specify in concomitant medication section)
2. Others (please specify)
3. No action taken

- Seriousness: Check either ‘yes’ or ‘no’ for the question, ‘Is this case under the criteria of serious adverse event?’ If ‘yes’, record the appropriate number for the category of seriousness.

A serious adverse event is any untoward medical occurrence at any dose that:

- results in death;

- is life-threatening;
- requires inpatient hospitalization or prolongation of hospitalization;

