9.2. Reporting Period

For each patient, the safety event reporting period begins at the time of the patient's first dose of PRISTIQ®, and lasts through the end of the observation period of the study, which must include at least 28 days following the last administration of a drug under study; a report must be submitted to Pfizer Safety (or its designated representative) for any of the types of safety events listed in the table above occurring during this period. If a patient was administered a drug under study on the last day of the observation period, then the reporting period should be extended for 28 days following the end of observation.

Most often, the date of data privacy statement is the same as the date of enrollment. In some situations, there may be a lag between the dates of data privacy statement and enrollment. In these instances, if a patient provides data privacy statement but is never enrolled in the study (e.g., patient changes his/her mind about participation), the reporting period ends on the date of the decision to not enroll the patient.

If the investigator becomes aware of a SAE occurring at any time after completion of the study and s/he considers the SAE to be related to PRISTIQ®, the SAE also must be reported to Pfizer Safety.

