8.2.1.2 Adverse Events

All adverse events reported after start of administration of PRISTIQ® will be considered as on-treatment and summarised. Adverse events reported with partial dates of onset will be assumed as on-treatment, unless month/year of AE onset date is before start date of PRISTIQ®.

In the safety analysis set, the number of subjects to whom AE occurred and the number of AEs will be calculated and the incidence rate of AEs will be estimated with its 95% confidence interval.

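### The plan promises safety data on 6-month users but sets no consistent adverse-event window for them beyond week 8, and the SAP counts adverse events with no end date

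*Protocol*

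**What the plan says.** **Long-term commitment.** Protocol 7.3.3.1 states: "Safety and effectiveness data of at least 60 subjects who have been administered PRISTIQ® over 6 months out of enrolled subjects will be collected". The same section says these data are to be analysed separately.

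**Observation period.** Protocol 7.1 states: "The observation period for each subject is from initiating administration of PRISTIQ® until week 8". Protocol 7.3.3 and SAP 2.1 repeat this. The one exception is for early stoppers: "If administration is discontinued before week 8, observation should be done for at least 28 days from the last administration day". Nothing comparable is written for subjects who continue.

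**AE collection.** Protocol 7.4.10.3 asks for safety events as specified in Section 9, "including all adverse events that occur during the observation period regardless of causal relationship to PRISTIQ".

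**Reporting period.** Protocol 9.2 has the period last through the end of observation, "which must include at least 28 days following the last administration of a drug under study". It then adds that if a patient was dosed on the last day of observation, "then the reporting period should be extended for 28 days following the end of observation". After study completion, 9.2 asks only for serious events that the investigator considers related.

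**Late recognition.** Protocol 7.3.3 says of an "adverse event/safety event recognized after the observation period ends, it should be recorded in the CRF", by reference to Section 9.

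**Effectiveness.** Protocol 7.4.9.1 and 7.4.9.2 add an assessment after 6 months. SAP 5.3 defines a long-term effectiveness set and SAP 8.2.2 its analyses. The SAP defines no long-term safety set.

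**AE analysis.** SAP 8.2.1.2 states: "All adverse events reported after start of administration of PRISTIQ® will be considered as on-treatment and summarised". It gives one incidence with a 95% confidence interval. SAP 8.2.1.3 splits AEs by administration below 180 days versus 180 days or more, and SAP 8.2.1.4 lists AEs of long-term subjects.

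**The concern.** Effectiveness was adapted for long-term use and safety was not. A site that reads the week-8 rule together with the 28-day extension could stop routine AE recording while the patient is still on drug. A site that reads the last-administration rule would carry on. With about 20 centres, both readings may be in use at once.

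Two results are exposed:

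- **Long-term safety.** In the safety set, SAP 8.2.1.1 measures exposure to the last administration date, or to the last date in the data if treatment continues. A subject can therefore be classed as a 180-day user although AE recording stopped near day 84. A first event in month 4 would then appear as AE-free long-term use.
- **The main AE incidence.** Where late events are recorded, they join a proportion in which other subjects were followed for much less time. The result has no defined time at risk.

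**Working it through.** The documents give no power or precision calculation to reproduce; 600 and 60 are set as requirements. The check is date arithmetic followed by an illustration.

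**Step 1: the two end points for a 180-day user**

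Inputs: week 8 (Protocol 7.1), 28 days (Protocol 9.2), and 6 months taken as 180 days (SAP 5.3).

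| Reading | Arithmetic | End of AE window |
|---|---|---|
| Week 8 only | 8 × 7 | day 56 |
| Still dosed at end of observation, extended 28 days | 56 + 28 | day 84 |
| At least 28 days after last administration | 180 + 28 | day 208 or later |

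The gap between the two readings of 9.2 is 208 − 84 = 124 days at least. On the day-84 reading, 180 − 84 = 96 treatment days are uncovered, and 96/180 = 53%.

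Early stoppers have their own end dates. Stopping on day 10 gives at least day 38, and stopping on day 55 gives at least day 83.

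**Step 2: does another section settle it?**

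- 7.3.3 sends late-recognised events to the CRF but relies on Section 9, which leads back to the two readings in 9.2.
- The after-completion rule in 9.2 covers related serious events only, so it cannot supply non-serious or unrelated AEs.
- The last-administration rule gives no fixed end for a patient who never stops.

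**Step 3: share of first events missed if recording stops at day 84**

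The AE risks are assumptions, since the documents give none. With 8-week risk p and a constant hazard, risk by day t = 1 − (1 − p)^(t/56).

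| p | Day 84 | Day 180 | Share of first AEs by day 180 that fall after day 84 |
|---|---|---|---|
| 10% | 14.6% | 28.7% | (28.7 − 14.6)/28.7 = 49% |
| 20% | 28.4% | 51.2% | (51.2 − 28.4)/51.2 = 44% |

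**Step 4: shift in the main incidence if late events are recorded and pooled**

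The comparator is a uniform 84-day window. Long-term users' AEs are counted to day 180, with 60 of 600 (10%) long-term users.

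- p = 20%: 0.9 × 28.4% + 0.1 × 51.2% = 30.7%, a shift of 2.3 points.
- p = 10%: 0.9 × 14.6% + 0.1 × 28.7% = 16.0%, a shift of 1.4 points.

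With 150 of 600 (25%, an assumed share) and p = 20%, the shift is 0.25 × (51.2 − 28.4) = 5.7 points.

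**Step 5: falling hazard**

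Keep p = 20% and halve the hazard after day 84. The daily hazard is −ln(0.8)/56 = 0.00398. Risk by day 180 is 1 − (1 − 0.284) × exp(−0.5 × 0.00398 × 96) = 40.9%. The shift with 60 of 600 is then 0.1 × (40.9 − 28.4) = 1.2 points, and the share of first events after day 84 is (40.9 − 28.4)/40.9 = 30%.

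**The case against.** The strongest reply is that the plan does provide a long-term window. Section 9.2 requires at least 28 days after last administration, which takes a 180-day user to day 208 or beyond. Section 7.3.3 sends later-recognised events to the CRF, and the table in 9.1 has all non-serious AEs recorded there. Section 7.3.3.1 also sits under the duration heading and can be read as the specific exception to the general week-8 rule. On the analysis side, the 180-day split and the long-term listing already exist. The study is descriptive, and SAP Section 4 lists hypotheses and decision rules as not applicable.

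Much of this stands. A reader might infer that observation ends at week 8 for every subject and that nothing is collected after day 84. The documents do not support that: early stoppers have their own rule, and day 84 is only one reading of 9.2. A reader might also infer that late events appear only in the pooled incidence; they would also reach the split and the listing.

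What the reply does not do is make the window consistent. 7.3.3.1 states the intent to collect but gives no period. The two sentences in 9.2 still give different dates for the same patient, and the later date conflicts with the week-8 definition. The split counts AEs from day 1, classifies subjects by exposure that is known only after baseline, and compares unequal follow-up without person-time. Subjects who stop because of an AE fall into the shorter group by construction.

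**Conclusion.** The concern holds as a contradiction, not as an absence. AE collection for subjects continuing past week 8 can end at day 84 or at day 208 and later, depending on which sentence of 9.2 is followed. As written, the separate long-term safety data promised in 7.3.3.1 cannot be relied on to be complete or comparable between sites.

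The 124-day gap and the uncovered 53% follow from the documents' own figures, the latter only on the day-84 reading. The effect on the main incidence is modest: about 1.4 to 2.3 points with 60 of 600 long-term users, assuming an 8-week risk of 10% to 20% and a constant hazard. It is smaller if the hazard falls and larger if more subjects continue. The constant hazard is a strong assumption for patients selected by staying on drug for 180 days. The long-term safety summary is affected more than the main rate.

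**What to change.** **Protocol.** Reconcile 7.1, 7.3.3, 7.3.3.1, 7.4.10.3 and 9.2 so that one explicit AE recording window applies to every subject who continues beyond week 8. It should agree with the last-administration-plus-28-days wording in 9.2 and state an end for those still on drug at the 6-month evaluation. It must cover all continuers, because long-term status is known only at day 180. Simply ending AE recording at the 6-month evaluation could cut below the 28-day floor in 9.2.

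**SAP 8.2.1.2.** Compute the main AE incidence from onsets within one fixed cut-off applied to all subjects. A subject who stops on day 10 need be observed only to day 38, so the SAP should also say how subjects observed for less than the cut-off are handled.

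**Long-term safety table.** For subjects with 180 days or more, tabulate AEs by onset before and after week 8. Give person-time rates in place of the unadjusted comparison of under 180 versus 180 days or more.

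**Cost.** A short amendment, one extra table and some extra CRF entry for subjects continuing past week 8. The 6-month effectiveness assessment already exists. Protocol Section 4 planned the end of data collection for 01 Dec 2018, and SAP version 4.0 is dated 08 Nov 2019. If collection has closed, only the analysis changes remain possible, and the report should state how far AE recording actually ran for long-term subjects.

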7.2. Study Size

600 patients will be enrolled in approximately 20 study centers in this study based on the MFDS re-examination regulation ([Section 7.3.3](#)). Most of the study centers would be general hospitals or psychiatric hospitals which have the accredited psychiatrists eligible for conducting PMS study.

Subjects will be enrolled by continuous registration method. It means that the physician should consecutively enroll all patients who are administered PRISTIQ® for the first time and satisfy the inclusion and exclusion criteria after contract is made and the study is initiated.

7.3. Setting

7.3.1. Inclusion criteria

- 1) Adults 19 years of age or older, who have been administered at least one dose of PRISTIQ® for the treatment of Major depressive disorder (MDD).

2) Patients who have been administered PRISTIQ® for the first time after signing the data privacy statement.

7.3.2. Exclusion criteria

Patients to whom PRISTIQ® is contraindicated as per the local labeling;

- 1) Hypersensitivity to desvenlafaxine succinate, venlafaxine hydrochloride or to any excipients in the PRISTIQ® formulation.
- 2) This drug must not be used in combination with a MAOI, or within at least 14 days of discontinuing treatment with a MAOI.

7.3.3. Duration of the study

According to MFDS re-examination regulation, the re-examination report based on collected data of 6 years must be submitted to MFDS within 3 months after the end of specified re-examination period (from the product approval date to 6 years afterwards). The re-exam period is from 06 February 2014 to 05 February 2020, and the final study report should be submitted by 05 May 2020.

The data collection period of this study is until the required subject number (600 patients) is collected. The observation period for each subject is from initiating administration of PRISTIQ® until week 8. If administration is discontinued before week 8, observation should be done for at least 28 days from the last administration day. All the data collected during the observation period should be recorded in the case report form (CRF). In case of an adverse event/safety event recognized after the observation period ends, it should be recorded in the CRF as specified in Section 9.

7.3.3.1. Long-term use study

As PRISTIQ® could be used in a long time considering its indication, data from the patients administered in a long time out of enrolled patients will be collected and analyzed separately. Safety and effectiveness data of at least 60 subjects who have been administered PRISTIQ® over 6 months out of enrolled subjects will be collected.

7.3.4. Dosage and administration

The use and dosage recommendations for PRISTIQ® should take place on the basis of the approved local product document. If subjects have been administered PRISTIQ® off label, they should be excluded from the safety analysis set and analyzed separately.

Refer to the most updated local product document for the detailed information on prescription.

7.4. Study Procedures

All patients who are eligible for this study will be enrolled and evaluated.

There will be no visit mandated, but at least once safety information should be followed up by visit, telephone, e-mail or fax etc. during the study. The investigator should record the following information on the patient's CRF:

